9.3.3. Secondary Endpoints

The comparison of cannula depths at the abdominal infusion site location will be analyzed as part of the mixed effects model described in Section [9.3.2](#).

9.3.4. Exploratory Endpoints

Local infusion site reaction data will be listed and summarized by infusion site location (Part A) **CCI** in frequency tables.

9.3.5. Safety Analyses

All treatment- and protocol procedure-related AEs will be listed, and if the frequency of events allows, safety data will be summarized using descriptive methodology. **CCI**

Symptoms reported to occur prior to enrolment will be distinguished from those reported as new or increased in severity during the study. Each symptom will be classified by the most suitable term from the Medical Dictionary for Regulatory Activities.

9.4. Interim Analysis

No interim analyses are planned for this study. If an unplanned interim analysis is deemed necessary for reasons other than a safety concern, the protocol must be amended.

9.5. Sample Size Determination

Approximately 46 participants with T1D will be enrolled in Study I8B-MC-ITTC so that approximately 40 participants complete Part A CCI of the study. CCI

Forty completing participants will provide approximately 80% power to demonstrate approximately a 55% increase in the VAS pain score between the infusion site locations in Part A CCI. Testing will be done at alpha-level of 0.05 with a 2-sided CI. The variability was estimated by analyzing a Lilly internal study that showed a log-scale standard deviation of within-subject difference in VAS pain scores of 0.95.

Participants who discontinue the study before completing the assessments may be replaced at the discretion of the sponsor and investigator to ensure that approximately 40 participants complete the study. The replacement participant will be assigned to the same treatment sequence as the discontinued participant.

10. Supporting Documentation and Operational Considerations

10.1. Appendix 1: Regulatory, Ethical, and Study Oversight Considerations

10.1.1. Regulatory and Ethical Considerations

- This study will be conducted in accordance with the protocol and with the following:
 - Consensus ethical principles derived from international guidelines including the Declaration of Helsinki and Council for International Organizations of Medical Sciences International Ethical Guidelines
 - Applicable International Conference for Harmonisation (ICH) Good Clinical Practice (GCP) Guidelines
 - Applicable laws and regulations
- The protocol, protocol amendments, ICF, IB, and other relevant documents (e.g., advertisements) must be submitted to an Institutional Review Board (IRB)/Independent Ethics Committee (IEC) by the investigator and reviewed and approved by the IRB/IEC before the study is initiated.
- Any amendments to the protocol will require IRB/IEC approval before implementation of changes made to the study design, except for changes necessary to eliminate an immediate hazard to study participants.
- Protocols and any substantial amendments to the protocol will require health authority approval prior to initiation except for changes necessary to eliminate an immediate hazard to study participants.
- The investigator will be responsible for the following:
 - Providing written summaries of the status of the study to the IRB/IEC annually or more frequently in accordance with the requirements, policies, and procedures established by the IRB/IEC
 - Notifying the IRB/IEC of SAEs or other significant safety findings as required by IRB/IEC procedures
 - Providing oversight of study conduct for participants under their responsibility and adherence to requirements of 21 Code of Federal Regulations (CFR), ICH guidelines, the IRB/IEC, European regulation 536/2014 for clinical studies (if applicable), and all other applicable local regulations
- Investigator sites are compensated for participation in the study as detailed in the Clinical Trial Agreement (CTA).

10.1.2. Informed Consent Process

- The investigator or his/her representative will explain the nature of the study, including the risks and benefits, to the participant or his/her legally authorized representative and answer all questions regarding the study.
- Participants must be informed that their participation is voluntary. Participants or their legally authorized representative will be required to sign a statement of informed consent that meets the requirements of 21 CFR 50, local regulations, ICH guidelines, Health Insurance Portability and Accountability Act requirements, where applicable, and the IRB/IEC or study center.
- The medical record must include a statement that written informed consent was obtained before the participant was entered in the study and the date the written consent was obtained. The authorized person obtaining the informed consent must also sign the ICF.
- Participants must be re-consented to the most current version of the ICF(s) during their participation in the study.
- A copy of the ICF(s) must be provided to the participant or the participant's legally authorized representative and is kept on file.
- Participants who are rescreened are required to sign a new ICF.

10.1.3. Data Protection

- Participants will be assigned a unique identifier by the sponsor. Any participant records, datasets, or tissue samples that are transferred to the sponsor will contain the identifier only; participant names or any information that would make the participant identifiable will not be transferred.
- The participant must be informed that his/her personal study-related data will be used by the sponsor in accordance with local data protection law. The level of disclosure must also be explained to the participant who will be required to give consent for his/her data to be used as described in the informed consent.
- The participant must be informed that his/her medical records may be examined by Clinical Quality Assurance auditors or other authorized personnel appointed by the sponsor, by appropriate IRB/IEC members, and by inspectors from regulatory authorities.
- The sponsor has processes in place to ensure data protection, information security and data integrity. These processes include appropriate contingency plan(s) for appropriate and timely response in the event of a data security breach.

10.1.4. Committees Structure

No committees are planned for this study.

10.1.5. Dissemination of Clinical Study Data

Communication of suspended for terminated dosing

If a decision is taken to suspend or terminate infusion of the excipients in the trial due to safety findings, this decision will be communicated by the sponsor to all investigators (e.g., through phone and/or email) as soon as possible. It will be a requirement that investigators respond upon receipt to confirm that they understand the communication and have taken the appropriate action prior to further dosing any participants with study intervention. Any investigator not responding will be followed up by the sponsor personnel prior to any further planned dosing. If an infusion is planned imminently, the sponsor personnel will immediately, and continually, use all efforts to reach investigators until contact is made and instructions verified.

Reports

The sponsor will disclose a summary of study information, including tabular study results, on publicly available websites where required by local law or regulation.

Data

The sponsor does not proactively share data from Phase 1 clinical trials. Requests for access to Phase 1 clinical trial data are evaluated on a case-by-case basis taking into consideration the ability to anonymize the data and the nature of the data collected.

10.1.6. Data Quality Assurance

- All participant data relating to the study will be recorded on printed or electronic CRF unless transmitted to the sponsor or designee electronically (e.g., laboratory data). The investigator is responsible for verifying that data entries are accurate and correct by physically or electronically signing the CRF.
- The investigator must maintain accurate documentation (source data) that supports the information entered in the CRF. Source data may include laboratory tests, medical records, and clinical notes.
- The investigator must permit study-related monitoring, audits, IRB/IEC review, and regulatory agency inspections and provide direct access to source data documents.
- Monitoring details describing strategy (e.g., risk-based initiatives in operations and quality such as risk management and mitigation strategies and analytical risk-based monitoring), methods, responsibilities, and requirements, including handling of noncompliance issues and monitoring techniques, are provided in the Monitoring Plan.
- The sponsor or designee is responsible for the data management of this study, including quality checking of the data.
- Source data may include laboratory tests, medical records, and clinical notes.
- The sponsor assumes accountability for actions delegated to other individuals (e.g., contract research organizations).

- Study monitors will perform ongoing source data verification to confirm that data entered into the CRF by authorized site personnel are accurate, complete, and verifiable from source documents; that the safety and rights of participants are being protected; and that the study is being conducted in accordance with the currently approved protocol and any other study agreements, ICH GCP, and all applicable regulatory requirements.
- Records and documents, including signed ICFs, pertaining to the conduct of this study must be retained by the investigator for the time period outlined in the CTA unless local regulations or institutional policies require a longer retention period. No records may be destroyed during the retention period without the written approval of the sponsor. No records may be transferred to another location or party without written notification to the sponsor.
- In addition, the sponsor or its representatives will periodically check a sample of the participant data recorded against source documents at the study site. The study may be audited by the sponsor or its representatives, and/or regulatory agencies at any time. Investigators will be given notice before an audit occurs.

Data Capture System

The investigator is responsible for ensuring the accuracy, completeness, legibility, and timeliness of the data reported to the sponsor.

An electronic data capture (EDC) system will be used in this study for the collection of CRF data. The investigator maintains a separate source for the data entered by the investigator or designee into the sponsor-provided EDC system. The investigator is responsible for the identification of any data to be considered source and for the confirmation that data reported are accurate and complete by signing the CRF.

Data collected via the sponsor-provided data capture systems will be stored by third parties. The investigator will have continuous access to the data during the study and until decommissioning of the data capture systems. Prior to decommissioning, the investigator will receive an archival copy of pertinent data for retention.

Data managed by a central vendor, such as laboratory test data, will be stored electronically in the central vendor's database system and reports/electronic transfers will be provided to the investigator for review and retention. Data will subsequently be transferred from the central vendor to the sponsor data warehouse.

Data from complaint forms submitted to the sponsor will be encoded and stored in the global product complaint management system.

10.1.7. Source Documents

- Source documents provide evidence for the existence of the participant and substantiate the integrity of the data collected. Source documents are filed at the investigator's site.

- Data reported on the CRF or entered in the eCRF that are transcribed from source documents must be consistent with the source documents or the discrepancies must be explained. The investigator may need to request previous medical records or transfer records, depending on the study. Also, current medical records must be available.
- Definition of what constitutes source data can be found in Section [10.1.6](#).

10.1.8. Study and Site Start and Closure

The study start date is the date on which the clinical study will be open for recruitment of participants.

The sponsor designee reserves the right to close the study site or terminate the study at any time for any reason at the sole discretion of the sponsor. Study sites will be closed upon study completion. A study site is considered closed when all required documents and study supplies have been collected and a study site closure visit has been performed.

The investigator may initiate study site closure at any time, provided there is reasonable cause and sufficient notice is given in advance of the intended termination.

Reasons for the early closure of a study site by the sponsor or investigator may include, but are not limited to:

- Failure of the investigator to comply with the protocol, the requirements of the IRB/IEC or local health authorities, the sponsor's procedures, or GCP guidelines
- Inadequate recruitment of participants by the investigator
- Discontinuation of further study intervention development.

If the study is prematurely terminated or suspended, the sponsor shall promptly inform the investigators, the IECs/IRBs, the regulatory authorities, and any contract research organization(s) used in the study of the reason for termination or suspension, as specified by the applicable regulatory requirements. The investigator shall promptly inform the participant and assures appropriate participant therapy and/or follow-up.

10.1.9. Publication Policy

In accordance with the sponsor's publication policy, the results of this study will be submitted for publication by a peer-reviewed journal if the results are deemed to be of significant medical importance.

10.2. Appendix 2: Clinical Laboratory Tests

- The tests detailed in the Safety Laboratory Tests table below will be performed by the central laboratory or by the local laboratory.
- Local laboratory results are only required in the event that the central laboratory results are not available in time for either study intervention administration and/or response evaluation. If a local sample is required, it is important that the sample for central analysis is obtained at the same time. Additionally, if the local laboratory results are used to make either a study intervention decision or response evaluation, the results must be entered into the CRF.
- In circumstances where the sponsor approves local laboratory testing in lieu of central laboratory testing (in the table below), the local laboratory must be qualified in accordance with applicable local regulations.
- Protocol-specific requirements for inclusion or exclusion of participants are detailed in Section 5 of the protocol.
- Additional tests may be performed at any time during the study as determined necessary by the investigator or required by local regulations.
- Pregnancy Testing will occur as indicated in the SoA (Section 1.3).

Investigators must document their review of the laboratory safety results.

Laboratory results that could unblind the study will not be reported to investigative sites or other blinded personnel.

Safety Laboratory Tests

Hematology ^a	Clinical Chemistry ^a
Hematocrit	Sodium
Hemoglobin	Potassium
Erythrocyte count (RBC)	Bicarbonate
Mean cell volume	Chloride
Mean cell hemoglobin	Calcium (ionized/total)
Mean cell hemoglobin concentration	Phosphorus/Phosphate
Leukocytes (WBC)	Magnesium
Absolute counts of:	Glucose
Neutrophils	Blood urea nitrogen (BUN)
Lymphocytes	Creatinine
Monocytes	Uric acid
Eosinophils	Total protein
Basophils	Albumin
Platelets	Total bilirubin
Urinalysis ^a	Alkaline phosphatase (ALP)
Specific gravity	Aspartate aminotransferase (AST)
pH	Alanine aminotransferase (ALT)
Protein	
Glucose	Hepatitis B surface antigen ^a
Ketones	Hepatitis C antibody ^a
Bilirubin	HIV ^a
Urobilinogen	Pregnancy test
Blood	FSH ^{a, b}
Nitrite	HbA1c ^a
Coagulation	
International normalized ratio (INR)	

Abbreviations: FSH = follicle-stimulating hormone; HbA1c = hemoglobin A1c; HIV = human immunodeficiency virus; RBC = red blood cells; WBC = white blood cells.

Note: Results of these assays will be validated by the local laboratory at the time of testing. Additional tests may be performed or auto-calculated by the laboratory as part of its standard panel that cannot be removed. Some of the above parameters are calculated from measured values. Omission of calculated values will not be considered as a protocol violation.

^a Performed at screening only.

^b Follicle-stimulating hormone test must be performed at screening for a woman who is less than 55 years of age with an intact uterus, not on hormone therapy and has had 12 months of spontaneous amenorrhea.

10.2.1. Blood Sampling Summary

Approximately 100 mL blood sampling per participant is expected in this study. Blood sampling estimate will be provided in the ICF.

10.3. Appendix 3: Adverse Events: Definitions and Procedures for Recording, Evaluating, Follow-up, and Reporting

10.3.1. Definition of AE

AE Definition

- An AE is any untoward medical occurrence in a participant administered a pharmaceutical product and which does not necessarily have a causal relationship with the study intervention. An AE can therefore be any unfavourable and unintended sign (including an abnormal laboratory finding), symptom, or disease (new or exacerbated) temporally associated with the use of a medicinal (investigational) product, whether or not related to the medicinal (investigational) product.

Events Meeting the AE Definition

- Any abnormal laboratory test results (hematology, clinical chemistry, or urinalysis) or other safety assessments (e.g., ECG, radiological scans, vital sign measurements), including those that worsen from baseline, considered clinically significant in the medical and scientific judgment of the investigator (i.e., not related to progression of underlying disease).
- Exacerbation of a chronic or intermittent pre-existing condition including either an increase in frequency and/or intensity of the condition.
- New conditions detected or diagnosed after study intervention administration even though they may have been present before the start of the study.
- Signs, symptoms, or the clinical sequelae of a suspected drug-drug interaction.
- Signs, symptoms, or the clinical sequelae of a suspected overdose of either study intervention or a concomitant medication. Overdose per se will not be reported as an AE/SAE unless it is an intentional overdose taken with possible suicidal/self-harming intent. Such overdose should be reported regardless of sequelae.

Events NOT Meeting the AE Definition

- Any clinically significant abnormal laboratory findings or other abnormal safety assessments that are associated with the underlying disease, unless judged by the investigator to be more severe than expected for the participant's condition.
- The disease/disorder being studied or expected progression, signs, or symptoms of the disease/disorder being studied, unless more severe than expected for the participant's condition.
- Medical or surgical procedure (e.g., endoscopy, appendectomy): the condition that leads to the procedure is the AE.
- Situations in which an untoward medical occurrence did not occur (social and/or convenience admission to a hospital).

- Anticipated day-to-day fluctuations of pre-existing disease(s) or condition(s) present or detected at the start of the study that do not worsen.
- Pain experienced at the infusion site during scheduled VAS assessments is not to be documented as an AE.

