1.2. Schema

1.3. Schedule of Activities (SoA)

Table 1 Trial Flow Chart

Trial Period	Screening Period		Study Period	Follow-up-Televisit/early discontinuation	Comments
Visit no.	0	1	2 (Part A) CCI	4	
Timing	≥1 day before Visit 1	≤28 days prior to Visit 2	at least 3 days between Visit 2 and Visit 3	CCI	
In-house Visit/Period			see Table 2	CCI	
Informed consent	X	X			At Visit 1, check that informed consent has been signed and dated
Fasting		X			
Inclusion/exclusion criteria		X			At Visit 2, confirm participant compliance
Demographic data		X			
Smoking and alcohol consumption habits		X			
Medical history/Pre-existing Conditions		X			
Weight		X	X		
Height		X			
Alcohol breath test/urine drug screen		X	X		
Physical examination		X			
Vital signs		X	X		
12-lead ECG		X			
Haematology		X			
Biochemistry		X			
Coagulation		X			
Urinalysis		X			
Infectious serology		X			

Trial Period	Screening Period		Study Period	Follow-up- Televisit/early discontinuation	Comments
Visit no.	0	1	2 (Part A) CCI	4	
Timing	≥1 day before Visit 1	≤28 days prior to Visit 2	at least 3 days between Visit 2 and Visit 3	CCI	
In-house Visit/Period			see Table 2	CCI	
Pregnancy test		X	X		Only required for women of childbearing potential Serum at the screening visit and urine at Visits 2 and 3
FSH		X			This is only for women with both more than 12 months of amenorrhea and age of ≤55 (see Sections 10.2 and 10.4)
HbA1c		X			
Ultrasound			X		Thickness of the subcutaneous (SC) fat layer will be assessed at the abdominal areas (lower right and left), arm, thigh, and buttock.
Local Infusion site pain (VAS)			X		See Table 2 and Table 3 for collection times
Local Infusion site reactions			X		After removal of each infusion set
CCI Platform			X		Collect image of each local infusion site prior to insertion and after removal of each infusion set
AEs/Product Complaints		X	X	X	
Concomitant Medications		X	X	X	

Trial Period	Screening Period		Study Period		Follow-up- Televisit/early discontinuation	Comments
Visit no.	0	1	2 (Part A) CCI		4	
Timing	≥ 1 day before Visit 1	≤ 28 days prior to Visit 2	at least 3 days between Visit 2 and Visit 3		CCI	
In-house Visit/Period			see Table 2	CCI		
Meals (breakfast, lunch, and dinner)			X			Breakfast will be provided prior to study activities. Lunch will be provided after completion of the first bolus assessments. Dinner will be provided after completion of the second bolus assessments

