8.2.5.3. Local Infusion Site Reactions

Symptoms or signs of local infusion site reactions may include erythema, induration, pain, pruritus, and edema.

Pre-specified local infusion site reaction assessments will be performed and collected at the time points indicated in the SoA (Section 1.3).

In addition, if a spontaneous ISR is reported by a participant or site staff at a non-prespecified time point, the local infusion site reaction eCRF will be used to capture additional information about this reaction (e.g., infusion site pain, erythema, induration, pruritis, and edema).

Local infusion site reactions, whether recorded as a result of the prespecified (or solicited) assessment or spontaneously reported reactions, will be recorded as AEs as clinically indicated.

Investigational site staff will be provided with separate instructions/training on how to evaluate local infusion site reactions and their severity in a consistent manner.

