10.3.2. Definition of SAE

If an event is not an AE per definition above, then it cannot be an SAE even if serious conditions are met (e.g., hospitalization for signs/symptoms of the disease under study, death due to progression of disease).

SAE is defined as any untoward medical occurrence that, at any dose:

a. Results in death

b. Is life-threatening

The term ‘life-threatening’ in the definition of ‘serious’ refers to an event in which the participant was at risk of death at the time of the event. It does not refer to an event, which hypothetically might have caused death, if it were more severe.

c. Requires inpatient hospitalization or prolongation of existing hospitalization

- In general, hospitalization signifies that the participant has been admitted to hospital for observation and/or treatment that would not have been appropriate in the physician’s office or outpatient setting. Complications that occur during hospitalization are AEs. If a complication prolongs hospitalization or fulfills any other serious criteria, the event is serious. When in doubt as to whether “hospitalization” occurred or was necessary, the AE should be considered serious.
- Hospitalization for elective treatment of a pre-existing condition that did not worsen from baseline is not considered an AE.

d. Results in persistent disability/incapacity

- The term disability means a substantial disruption of a person’s ability to conduct normal life functions.
- This definition is not intended to include experiences of relatively minor medical significance such as uncomplicated headache, nausea, vomiting, diarrhea, influenza, and accidental trauma (e.g., sprained ankle) which may interfere with or prevent everyday life functions but do not constitute a substantial disruption.

e. Is a congenital anomaly/birth defect

- Abnormal pregnancy outcomes (e.g., spontaneous abortion, fetal death, stillbirth, congenital anomalies, ectopic pregnancy) are considered SAEs.

f. Other situations:

- Medical or scientific judgment should be exercised in deciding whether SAE reporting is appropriate in other situations such as important medical events that may not be immediately life-threatening or result in death or hospitalization but may jeopardize the participant or may require medical or surgical intervention to prevent one of the other outcomes listed in the above definition. These events should usually be considered serious.

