9.3.4 Adverse Events

Where changes in severity are recorded in the Case Report Form, each separate severity of the adverse event (AE) will be reported in the listings, only the most severe will be used in the summary tables. A pre-existing condition is defined as an AE that starts before the participant has provided written informed consent and is ongoing at consent. A non-treatment emergent AE is defined as an AE which starts after informed consent but prior to dosing. A treatment-emergent AE is defined as an AE which occurs postdose or which is present prior to dosing and becomes more severe postdose.

All AEs will be listed. Treatment-emergent AEs will be summarized by study part and by infusion site location/study treatment, severity, and relationship to the study drug/protocol procedure. The frequency (the number of AEs, the number of participants experiencing an AE and the percentage of participants experiencing an AE) of treatment-emergent AEs will be summarized by infusion site location/study treatment, Medical Dictionary for Regulatory Activities (MedDRA) version 24.0 system organ class, and preferred term. The summary and frequency AE tables will be presented for all causalities and those considered related to the study drug by the investigator and repeated for those considered related to the protocol procedure. Any serious AEs will be listed. Summaries by infusion site location/study treatment will only be possible where a particular AE is able to be attributed to a particular infusion site location, AE data will also be summarized by study part.

Discontinuations due to AEs will be listed.

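### Pain at a scheduled VAS rating is exempt from AE recording without exception, so it can be neither an AE nor an SAE, and a withdrawal it causes stays out of the AE-discontinuation listing

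*Protocol*

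**What the plan says.** - **Protocol 10.3.1**, under events not meeting the AE definition: "Pain experienced at the infusion site during scheduled VAS assessments is not to be documented as an AE". No exception follows. Two neighbouring exclusions in the same list, for abnormal findings tied to the underlying disease and for the disease under study, are lifted when the event is more severe than expected.
- **Protocol 10.3.2**: "If an event is not an AE per definition above, then it cannot be an SAE even if serious conditions are met".
- **Protocol 8.2.5.3**: "Symptoms or signs of local infusion site reactions may include erythema, induration, pain, pruritus, and edema". Such reactions, "whether recorded as a result of the prespecified (or solicited) assessment or spontaneously reported reactions, will be recorded as AEs as clinically indicated". A separate form captures details "if a spontaneous ISR is reported by a participant or site staff at a non-prespecified time point".
- **Protocol 1.3**: the solicited reaction check is scheduled "After removal of each infusion set", at about +11.5 h in Table 2.
- **Protocol 8.3 and 10.3.4**: the duty to follow up events that made a participant stop the infusion applies to events meeting the AE, SAE or product complaint definitions. Intensity grading and causality assessment are required for AEs and SAEs.
- **SAP 9.3.4**: "Discontinuations due to AEs will be listed". Treatment-emergent AEs are tabulated by severity and relationship.
- **SAP 9.3.1, 9.3.3 and 9.2**: VAS scores are listed and tabulated in categories up to 46 to 100 mm, categorical reaction pain is tabulated by site, and disposition is summarised and listed.

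**The concern.** Infusion-site pain is the effect this trial sets out to provoke and measure. It is sensible not to turn every scheduled score into an AE, because that would count the primary endpoint twice. But the exemption is written by the moment of the rating and not by what the pain leads to. Pain at a scheduled rating that makes someone leave, needs treatment, or meets a seriousness criterion is exempt on the same terms as a score of 5 mm.

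Section 8.2.5.3 leaves AE recording of a pain reaction to clinical judgment. Section 10.3.1 withdraws that judgment at the scheduled ratings, and neither section refers to the other. Two sites could record the same episode differently, and a reader of the AE section of the report could not tell whether an absence of pain-related discontinuations is a finding or a product of the recording rule.

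**Working it through.** No planned figure is at issue, so this is a comparison of rules with two counts from Protocol Table 2.

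**1. How many ratings are exempt.** Inputs: 5 sites, 3 boluses per site, and ratings at -5, +1 and +15 min.
- All ratings: 5 × 3 × 3 = 45 per participant.
- Post-bolus ratings: 5 × 3 × 2 = 30 per participant.

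**2. Whether the solicited reaction check would pick up the same pain.** The last boluses at sites 1 to 5 are at +9.0, +9.5, +10.0, +10.5 and +11.0 h, and the check is at +11.5 h. The gap is (11.5 − bolus hour) × 60 min.

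| Site in sequence | Last bolus (h) | Gap to check (min) |
|---|---|---|
| 1 | 9.0 | 150 |
| 2 | 9.5 | 120 |
| 3 | 10.0 | 90 |
| 4 | 10.5 | 60 |
| 5 | 11.0 | 30 |

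Protocol 2.1 describes bolus pain as immediate and subsiding over 20 to 30 minutes. The check falls after that span at sites 1 to 4 and at its edge at site 5. For the first and second boluses it falls at least 3 h later still. It would usually miss bolus pain.

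**3. Whether the spontaneous route fills the gap.** It applies to reports at time points that are not prespecified. The +1 and +15 min ratings are prespecified. Pain reported between ratings, or after +15 min, can enter this way. Pain reported only at a rating has no clear route.

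**4. One case followed through the rules.** Suppose a participant marks a high score at +1 min and withdraws because of it, as Protocol 7.2 allows at the participant's own request.

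| Output or duty | Result as written |
|---|---|
| VAS listing and category table (SAP 9.3.1) | Score appears |
| Disposition (SAP 9.2) | Withdrawal appears; the SAP text does not say that pain is shown as a reason |
| AE record, causality, AE follow-up (Protocol 8.3, 10.3.4) | None, by 10.3.1 |
| SAE status | Barred, by 10.3.2 |
| Treatment-emergent AE tables (SAP 9.3.4) | No entry |
| Listing of discontinuations due to AEs (SAP 9.3.4) | No entry |

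The score and the withdrawal are each kept. No output specified in the SAP ties one to the other.

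**The case against.** The best defence is that the two sections mostly govern different moments. Section 8.2.5.3 says only that reactions "will be recorded as AEs as clinically indicated", so it does not make every pain reaction an AE, and its solicited check is a separate assessment after set removal. A specific exemption beside a general, discretionary rule can be read as consistent. This stands in large part. A reader might infer that sites receive directly opposite instructions, but the text does not go that far. The true overlap is pain present at a scheduled rating that also persists, is reported spontaneously or has consequences.

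It can also be said that the pain is well documented elsewhere. This stands too. A reader might infer that such pain disappears from the safety tables or that its intensity goes unrecorded. It does not: the VAS is itself an intensity measure, and the SAP places it under safety and tolerability. Medication given for pain would be recorded with its reason (Protocol 6.5) and listed (SAP 9.3.5).

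Finally, serious pain would probably outlast a single rating, and Protocol Section 8 requires immediate safety concerns to be discussed with the sponsor. That makes the SAE consequence remote. It does not remove a rule that says seriousness is irrelevant once the AE exemption applies.

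**Conclusion.** The point holds as a recording gap. Read as written, Sections 10.3.1 and 10.3.2 deny AE and SAE status to pain at any of the 45 scheduled ratings, whatever follows from it, and this is not reconciled with Section 8.2.5.3. The loss is confined to classification, the causality assessment and follow-up tied to it, and the entry in the AE-discontinuation listing.

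How many participants this would affect is unknown. A reader might take the gap between 46 randomised and 40 completing, 6/46 = 13%, as the number of pain-driven losses that could be hidden. The documents do not support that: it is a planning allowance with no stated reasons, and the statement of which parts must be completed is partly redacted. Nor do they provide for stopping a single site because of pain; Protocol 6.1.2 names occlusion and cannula pull-out. Withdrawal at the participant's own request is the scenario the text supports.

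The conclusion assumes that sites apply the exemption literally, and that the table and listing shells, which are not among the documents, do not already show pain as a reason for withdrawal. It is a modest defect, worth correcting because pain is the main outcome and the correction is cheap.

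**What to change.** 1. In Protocol 10.3.1, keep the exemption for pain that is only rated on the VAS. Add that infusion-site pain is recorded as an AE, whatever the time of the rating, when it leads to withdrawal or to stopping an infusion, leads to concomitant treatment, or meets a criterion in 10.3.2.
2. Cross-refer 10.3.1, 10.3.2 and 8.2.5.3 so that it is clear which governs.
3. In SAP 9.3.4, add a listing of discontinuations due to infusion-site pain.

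This concerns recording only and sets no rule for stopping or treating. It costs about one sentence with its cross-references and one listing. The downside is a few more AE records and a slightly less favourable AE table.
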